2.1. Summary of the Proposed Study

This protocol is for a randomized, double-blind, active placebo controlled study of the safety and efficacy of 3,4-methylenedioxymethamphetamine MDMA-assisted psychotherapy in patients with treatment-resistant posttraumatic stress disorder (PTSD). In this study, 12 patients will receive either an active placebo dose or a fully active dose of MDMA during three experimental psychotherapy sessions, each six to eight hours long, scheduled three to five weeks apart. Participants assigned to receive the active placebo and participants assigned to receive the fully active dose will receive the same course of psychotherapy, which consists of two introductory sessions prior to the first experimental (active placebo or fully active dose MDMA) session, follow-up psychotherapy sessions occurring a day after each experimental session, and two to four integrative psychotherapy sessions conducted on a weekly basis after each experimental session, with the first of these sessions scheduled a week after each experimental session. Active placebo will be 25 mg MDMA followed two and a half hours later by 12.5 mg, and the fully active dose will be 125 mg followed two and a half hours later by 62.5 mg. Extent of PTSD symptoms will be assessed by an independent rater at baseline, 3 weeks after the second and third experimental session and two, six and 12 months after the third MDMA-assisted session. The Clinician Administered PTSD Scale (CAPS) will serve as the primary outcome measure. We hypothesize that PTSD symptoms will be reduced in participants receiving the fully active dose of MDMA, that MDMA-assisted psychotherapy will be well-tolerated and will not produce serious adverse effects in this population, that three experimental sessions will lead to better results than two sessions, and that results are stable at the follow up assessments at 2, 6 and 12 months after the last experimental session.

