2.5. Study Design

This study will employ a randomized, double-blind, active placebo-controlled design. Twelve patients with treatment-resistant PTSD will be randomly assigned after baseline assessment to either 3 MDMA-assisted sessions with a full dose of 125mg MDMA followed by a supplemental dose of 62.5mg MDMA administered 2.5 h later, or to an active placebo dose of 25mg MDMA followed by 12.5mg MDMA 2.5h later. Participants will undergo three sessions of MDMA-assisted psychotherapy scheduled to occur three to five weeks apart, 1 non-drug-psychotherapy session 24 h after each MDMA-session and 2-4 weekly, integrative psychotherapy sessions after each MDMA session. PTSD symptoms will be assessed by an independent assessor once prior to MDMA-assisted psychotherapy, 3 weeks after the second MDMA-assisted session, 3 weeks after the third experimental session, marking the end of non-drug psychotherapy, and two, six and twelve months later, with the CAPS serving as a primary outcome measure. Participants assigned to the active placebo condition will be given the opportunity to take part in an open-label continuation of the study, referred to here as “Stage 2.” Data gathered 3 weeks after the third experimental session will be treated as the baseline for Stage 2, and outcome measures will be administered 3 weeks after the second and third experimental session, 2, 6, and 12 months after baseline for all patients who consent to take part in Stage 2. Participants receiving the full dose in either Stage 1 or Stage 2 and not responding with significant improvement will be offered the opportunity to take part in an open-label continuation of the study, referred to as “Stage 3”, consisting of 2 additional MDMA sessions. During these sessions, they may receive 125 mg followed 2.5 hours later by 62.5 mg MDMA, or a 20% larger dose of 150 mg MDMA, followed by a supplemental dose of 75 mg administered 2.5 hours later. Outcome measurements gathered at 2 months after the third experimental session will serve as baseline measures for Stage 3. Procedures for non-drug psychotherapy sessions, experimental sessions and outcome measure administration will be the same as those employed in the first stage of the study.

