With participants carefully monitored for any indicators of adverse events, the initial doses of either 125 mg or 150 mg, and the cumulative dose of 187.5 mg or 225 mg respectively will prove to be tolerable and pose no more than minimal risk. The side effect profile is expected to increase with the higher dose but it is considered unlikely that there will be any Serious Adverse Events (SAEs) or any persisting side effects.

Table 1. Dose Regimen

	Initial Dose	Supplemental Dose	Cumulative Dose
Low Dose	25 mg	12.5 mg	37.5 mg
Fully Active Dose	125 mg	62.5 mg	187.5 mg
20% Larger Active Dose	150 mg	75 mg	225 mg

Supplemental doses for both the Low and the Fully Active dose conditions were chosen to be half the size of initial doses, and the dosage and schedule of dosing was chosen on the basis of case reports describing the use of MDMA in psychotherapy (Greer and Tolbert 1998; Stolaroff 2004, Styk 2007). Supplemental dosing performed 2.5 hours after the initial dose is expected to extend the course of drug effects without increasing their intensity. Both the Low and Fully Active dose conditions use supplemental doses that are half of the initial dose, to make dosing schedule equivalent across the conditions.

Participants will receive an initial dose of MDMA approximately 1 to 1.5 hours after they arrive at [name] office for each experimental session. If the investigators believe the participant is able to tolerate a supplemental dose and the participant agrees to take it, then a supplemental dose will be offered 2.5 hours later. The investigators will not administer the supplemental dose if the participant is exhibiting signs or symptoms that would place him or her at greater risk of experiencing a serious adverse event.

Each dose will consist of the specified amount of racemic MDMA mixed with an inactive substance, such as lactose, to prevent the investigators from distinguishing doses through weight or appearance of the capsules. Initial doses will be distinguished from supplemental doses through labeling them "Dose 1" and "Dose 2" or "first" and "second" dose to ensure that the correct dose is administered at the scheduled time. Each dose of MDMA will be administered along with 250 to 300 mL electrolyte-containing fluid. MDMA will be administered during each of the three experimental sessions, with the second and third session scheduled to fall two to four weeks after the previous experimental session.

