2.8.4. Methods and Schedule of Events

Table 2: Schedule of events:

Time																	
	h=hour																
	d=day																
	w=week																
	m=month																
weeks from start	-4 to -2	0	1	2	3	3 + 1 d	4	5	6	6 + 1 d	7	8	9	9	9 + 1 d	10	11
Medical Exam	x															x	
Informed consent	x																
SCID	x																
Metabol. profile, Thyroid Panel	x															x	
Liver Enzymes	x															x	
ECG	x																
Urine Drug Screen ³	x					x				x				x		x	x
Urine Pregancy Screen	x					x				x				x			
EEG/ Startle	x															x	
SCID	x														x	x	x
CAPS		x										x			x	x	x
PDS		x				x				x			x		x	x	x
RRPQ																	x
Nondrug Therapy			x	x		x	x	x		x	x	x		x	x	x	x ²
MDMA Therapy					x				x				x				
Vital Signs	x				x				x				x				
SUDS					x				x			x		x			
Both			x ¹	x ¹	x	x			x	x			x	x			

therapists present																
--------------------	--	--	--	--	--	--	--	--	--	--	--	--	--	--	--	--

x¹: Both therapists present at either one of the two introductory sessions.

x²: A half-hour closing meeting with the investigators; Participants learn condition assignment.

³: Urine drug testing will be done once additionally at random during the treatment phase

The study consists of eleven non-drug psychotherapy sessions, three sessions of MDMA-assisted psychotherapy, and five separate administrations of outcome measures (see Table 2). Most non-drug psychotherapy sessions will be scheduled on a weekly basis, and the three experimental sessions will be scheduled three to five weeks apart. The open-label continuation of the study (“Stage 2”) will be nearly identical in structure to the active-placebo controlled study except that only one introductory session is scheduled prior to the first experimental session. MDMA-assisted therapy will be performed by [name] and [name], a female co-therapist. Both therapists will also be present during one of the introductory therapy sessions and during each of the three psychotherapy sessions scheduled to occur 24 hours after each MDMA-assisted psychotherapy session. After psychiatric and medical screening, a total of 14 visits will occur according to Table 2.

2.8.5. *Nature of MDMA-assisted Psychotherapy*

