4.0 Study design

The study followed a randomized, active placebo-controlled, double-blind design, with subjects, psychotherapists and independent raters blinded to participant condition. Twelve subjects with treatment-resistant PTSD were randomly assigned after baseline assessment to receive either full dose of 125 mg MDMA followed by a supplemental dose of 62.5 mg MDMA administered 2.5 h

later, or to an active placebo dose of 25 mg MDMA followed by 12.5mg MDMA 2.5h later. Participants underwent three sessions of MDMA-assisted psychotherapy scheduled to occur three to five weeks apart, 1 non-drug-psychotherapy session 24 h after each MDMA-session and 2-4 weekly integrative psychotherapy sessions after each MDMA session. PTSD symptoms were assessed by an independent rater once prior to MDMA-assisted psychotherapy, three weeks after the second MDMA-assisted session, three weeks after the third experimental session. After unblinding, active placebo participants had the opportunity to take part in an open-label continuation of the study, referred to here as "Stage 2." Data gathered three weeks after the third experimental session was treated as the baseline for Stage 2, and outcome measures were administered three weeks after the second and third experimental session. Originally outcome measures would also be given two, six and twelve months after the third experimental session, but the six-month evaluations were discontinued after January 2009 in line with the Amendment 5 of the protocol. Participants receiving the full dose in either Stage 1 or Stage 2 who did not show significant improvement in PTSD symptoms were offered the opportunity to take part in an open-label continuation of the study, "Stage 3", consisting of two additional MDMA sessions. During these sessions, they could receive 125 mg followed 2.5 hours later by 62.5 mg MDMA or a 20% larger dose of 150 mg MDMA, followed by a supplemental dose of 75 mg administered 2.5 hours later, unless contraindicated by safety parameters. Outcome measurements gathered at 2 months after the third experimental session will serve as baseline measures for Stage 3. Stage 3 was also cancelled in line with Amendment 5. Of the 12 participants who completed the study, only three participants underwent Stage 3.

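### Protocol 2.8.1 allows two to four weeks between Stage 1 sessions, against three to five weeks elsewhere; a 14-20 day gap would put the T1 CAPS after session 3

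*Protocol*

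**What the plan says.** Protocol 2.8.1 states the Stage 1 interval as "with the second and third session scheduled to fall two to four weeks after the previous experimental session". Four other places give a longer one for the same three sessions:

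- Protocol 2.1: "each six to eight hours long, scheduled three to five weeks apart".
- Protocol 2.5: "Participants will undergo three sessions of MDMA-assisted psychotherapy scheduled to occur three to five weeks apart".
- Protocol 2.8.4: "the three experimental sessions will be scheduled three to five weeks apart".
- SAP 4.0, in the past tense: "Participants underwent three sessions of MDMA-assisted psychotherapy scheduled to occur three to five weeks apart".

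Protocol 2.8.2 times T1 at three weeks after session 2 and T2 at three weeks after session 3. No sentence there or in 2.8.3 says that T1 must come before session 3 dosing.

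For open-label Stage 2, Protocol 2.8.6 again gives two to four weeks between three sessions. Yet 2.8.4 calls that stage "nearly identical in structure to the active-placebo controlled study", with fewer introductory sessions as the only stated exception. Stage 3 (Protocol 2.8.7) also uses two to four weeks, but it has two sessions and its CAPS follows the second, so no order problem arises there.

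**The concern.** Section 2.8.1 is where site staff would look for the dosing interval, so its wording is an operative rule. If it is followed at its short end, T1 is taken after the third session and stops being a two-session measurement.

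Three things depend on T1:

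- Question and hypothesis 3 in Protocol 2.6, that three sessions do better than two. Protocol 2.8.3 expects lower CAPS after session 3 than after session 2 and names a paired Wilcoxon test for treatment-group contrasts. SAP 3.0 repeats the question.
- The SAP primary objective (3.1), which lists the CAPS three weeks after session 2.
- The SAP main analysis (6.4.1), a repeated-measures ANOVA over baseline, T1 and T2.

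In Stage 2, the CAPS after the second session is part of a secondary objective (SAP 3.2).

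**Working it through.** **Inputs.** T1 = session 2 + 21 days and T2 = session 3 + 21 days (Protocol 2.8.2). The session 2-3 gap is g days: 14 to 28 under Protocol 2.8.1, and 21 to 35 under Protocol 2.1, 2.5, 2.8.4 and SAP 4.0. The plan gives no figure of its own to reproduce.

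**Position of T1.** Days from session 3 to T1 = 21 - g.

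| Gap g (days) | T1 relative to session 3 |
|---|---|
| 14 | 7 days after |
| 20 | 1 day after |
| 21 | same day |
| 22 | 1 day before |
| 28 | 7 days before |
| 35 | 14 days before |

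Of the 15 whole-day gaps that 2.8.1 permits, 7 (14 to 20) put T1 after session 3. Of the 15 permitted by three to five weeks, none does: one (day 21) coincides and 14 put T1 first. These are counts of permitted gaps, not frequencies in patients. Only the session 2-3 gap matters; a short session 1-2 gap does not move T1 past session 3.

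**What the contrast then compares.** T2 stays 21 days after session 3 whatever g is. For a patient with g of 14 to 20, T2 minus T1 compares 21 days with 7 to 1 days after the same third session, not three sessions with two.

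**What the rest of the schedule implies.** Protocol 2.8.4 says: "The study consists of eleven non-drug psychotherapy sessions, three sessions of MDMA-assisted psychotherapy, and five separate administrations of outcome measures". Eleven, less 2 introductory and 3 next-day sessions, leaves 6 integrative sessions, or 6/3 = 2 per dosing session. At weekly spacing these fall on days 7 and 14, with the next weekly slot on day 21. Protocol 2.1 allows "two to four integrative psychotherapy sessions conducted on a weekly basis after each experimental session"; four would reach day 28 and cannot fit in a two-week gap. Table 2 has dosing at weeks 3, 6 and 9, lists week 9 twice, and in the damaged extract shows the second CAPS mark one column before the third MDMA mark. All this points to at least three weeks, with T1 first. But 9 - 6 = 3 weeks = 21 days, so T1 and session 3 fall due together with no slack.

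**Size and direction (illustration only; k and f are assumed).** Suppose k of the 8 planned full-dose patients (Protocol 2.8.1) are affected, and their T1 already shows a share f of the session-3 change. The mean T2-T1 contrast retained is 1 - f × k/8. If T1 is transiently worse, f is negative.

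- k = 2, f = 0.25: 1 - 0.25 × 2/8 = 94%. With f = -0.25: 106%.
- k = 4, f = 0.5: 1 - 0.5 × 4/8 = 75%. With f = -0.5: 125%.

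The documents give neither k nor f.

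**The case against.** The strongest reply is that this is a slip in one phrase. Three other protocol sections and the SAP agree on three to five weeks, the label of T1 ties it to the second session, and Table 2 appears to place it before the third. SAP 4.0 describes sessions scheduled at the longer interval, and SAP 6.2 already provides for procedures out of range and for analyses with and without deviations. The SAP describes a completed trial, with preliminary data already presented (SAP 8.0), so rewording cannot change conduct. Hypothesis 3 is also an uncontrolled within-arm comparison, which mixes session 3 with elapsed time and further psychotherapy in any case.

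Most of this stands and limits the weight of the point. It does not remove it. A 14-20 day gap with T1 on day 21 complies with 2.8.1 and 2.8.2 as written, so it may not be listed as a deviation unless someone looks. The 21-day tie also remains under the longer interval, because Table 2 suggests an order that no sentence states.

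A reader might infer that the error biases the three-versus-two contrast toward no difference. The documents do not support that. Early benefit would shrink the contrast, but Protocol 2.8.5.2 plans daily calls for a week after each session to look for continuing distress, and 2.8.8 provides rescue medication for severe distress after a session. A T1 in that week could be transiently worse, which would enlarge the apparent gain to T2.

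**Conclusion.** The conflict over the Stage 1 interval is certain, and the calendar consequence is exact: under 2.8.1 the T1 CAPS can fall up to 7 days after session 3. It exposes the T1 value, the T2-versus-T1 contrast and the SAP analyses that include T1. The direction of any distortion is unknown. In Stage 2 the same wording exposes a SAP secondary objective.

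Two further inferences would go too far. One is that patients' T1 data were in fact compromised: no document gives session dates or shows a gap under 21 days. The other is that the comparison of arms at T2 is spoiled: T2 is timed from session 3 and the spacing rule is the same in both arms. The converse is not safe either, because the SAP main ANOVA includes T1 and so cannot be called wholly unaffected.

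Severity is minor to should-fix. This rests on T1 being taken on its nominal day 21, since the protocol gives no visit window.

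**What to change.** - In Protocol 2.8.1, change the interval to three to five weeks; change 2.8.6 (Stage 2) to match. Section 2.8.7 (Stage 3) can stand.
- In Protocol 2.8.2, state that the CAPS after session 2, in Stages 1 and 2, is completed before session 3 dosing. This also settles the 21-day tie.
- For data already collected, check the actual session and T1 dates, and the Stage 2 equivalents. List any session 2-3 gap under 21 days, or any T1 taken after session 3, as a deviation under SAP 6.2. Name the session gap explicitly, because a T1 on day 21 is not itself late.
- Run the main ANOVA and the T2-versus-T1 contrast with and without those patients. The paired Wilcoxon test appears only in Protocol 2.8.3, so the SAP should name it if that contrast is to be reported.

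The cost is two interval corrections, one sentence on order, one check of dates and, if any such patient is found, a repeat run of two analyses. No new visits or procedures are needed.

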2.8.2. Assessments and Measures

Psychiatric diagnoses will be made through the Structured Clinical Interview for Diagnoses (SCID), and PTSD symptoms will be measured by the Clinician Administered PTSD Scale (CAPS) during screening to determine whether an individual may participate in the study.

PTSD symptoms will be assessed six times in this study:

- T0: *Baseline assessment*
- T1: *Post MDMA 2 assessment*: 3 weeks after the second experimental session (MDMA 2)
- T2: *End of treatment assessment*: 3 weeks after the third experimental session (MDMA 3)
- T3: *1st follow-up assessment*: 2 months after the third experimental session (MDMA 3)

T4: *2nd follow-up assessment*: 6 months after the third experimental session (MDMA 3) for all participants assigned to the Fully Active Dose condition, and all participants assigned to the Low Dose condition who choose not to take part in the open-label study continuation.

T5: *3rd follow-up assessment*: 12 months after the third experimental session (MDMA 3) for all participants assigned to the Fully Active Dose condition, and all participants assigned to the Low Dose condition who choose not to take part in the open-label study continuation.

Participants who choose to take part in the open label study continuation “Stage 2” will be assessed identically to stage 1 three weeks after the second and third (end of treatment) experimental sessions and two, six and twelve months after the third experimental session in Stage 2. The T2 assessment will serve as baseline for stage 2.

Participants who choose to take part in the open label study continuation “Stage 3” will be assessed identically to stage 1 three weeks after the second (end of treatment) experimental session and two, six and twelve months after the experimental session in Stage 2. The T3 assessment will serve as baseline for stage 3.

All outcome measures will be administered by an independent assessor. The independent assessor will remain blind to subject condition and will not be present during psychotherapy sessions. The CAPS will serve as the primary outcome measure, and the PDS will serve as additional measure of PTSD symptoms. The CAPS and the PDS are specifically designed to assess PTSD. German versions of all measures will be used in this study.

Degree of psychological distress will be assessed during the course of each experimental (Low or Fully Active Dose MDMA) session with a simple, one-item visual analog scale, the Subjective Units of Distress (SUDS). The participant’s beliefs concerning his or her condition assignment will be assessed during the non-drug psychotherapy session occurring a day after each experimental session. Neither of these measures will be treated as outcome measures. The first is intended to monitor the participant’s emotional state throughout the experimental session, and the second measure will be used to assess the degree to which the blind remains intact.

Response to study participation and perceived degree of choice in taking part in the study will be assessed with the Reactions to Research Participation Questionnaire (RRPQ), administered along with outcome measures two months after the third experimental session. The RRPQ is intended to assess the participant’s experience as a research subject, perceived reasons for consenting to be a research participant, and perceived freedom to take part in the study. The RRPQ will not serve as an outcome measure.

A brief description of each measure follows below, including its purpose in the study:

1. Clinician-Administered PTSD Scale CAPS (Blake et al., 1990). The CAPS is a structured clinical interview designed to assess the seventeen symptoms of PTSD along with eight associated features. The CAPS provides a means to evaluate (a) the frequency and intensity dimensions of each symptom (b) the impact of symptoms on the patient's social and occupational functioning (c) the overall severity of the symptom complex (d) global improvement since baseline and the validity of the ratings obtained. The CAPS interviews have been determined to have good internal consistency, concurrent validity, and test/retest reliability (Blake et al., 1990; Nagy et al., 1993). The CAPS was translated to German and tested with accident victims. The internal consistency of the German translation proved to be comparable to that of the original English version (Cronbach’s alpha = .88) (Schnyder U, Moergeli, H 2002). The CAPS will serve both as a screening measure and as a primary outcome measure.

2. Posttraumatic Diagnostic Scale PDS (Foa et al. 1993; Foa et al. 1997). The PDS is a 49-item self-report measure assessing presence of PTSD symptoms as described in DSM-IV, including type of traumatic event, length since the event occurred, degree of distress, and presence of intrusive thoughts, avoidance, and hypervigilance. The PDS also assesses duration of symptoms, and degree of impairment. A Cronbach alpha for the symptom severity scale is reported to be 0.92, and 0.91 for the whole scale, and test-retest reliability of 0.74 after two-week and one month intervals was 0.74. A translation into German was made by Ehlers 1996. This test has not yet been validated for German populations. This measure will serve as an additional outcome measure.
3. Reactions to Research Participation-Questionnaire-Short Form (Revised) RPQR (Newman and Kaloupek, 2001). This is a 24-item assessment of participants' experience of study participation, reasons for participation, and perceived costs and benefits of participation. The measure includes items addressing participation due to perceived coercion or undue influence by the investigators. A German translation will be developed for the study.
4. SCID-II (First et al. 1994). The SCID is a semi-structured interview, typically performed by a psychiatrist that permits accurate diagnosis of lifetime and current psychiatric disorders, using DSM-IV criteria. It will be used as a screening measure only.
5. Participant Beliefs on Condition Assignment: All participants will be asked to indicate whether they believe they have received active placebo or fully active doses of MDMA during the experimental sessions. This measure will serve as a means of measuring the success of study blinding for participants and investigators.
6. Subjective Units of Distress: This is a standardized subjective rating scale by which a participant can quickly rate comfort level throughout the session (1-7 scale). The parameters of the scale are explained at study initiations. This measure will serve as a means of safety monitoring during experimental sessions.

All sessions – introductory, MDMA-assisted sessions and integrative sessions - will be video recorded in their entirety. These recordings will be used for further analysis of patient behaviour, defence mechanisms, therapist interventions, manual adherence, etc. Patients will be asked to sign a separate video-IC. Patients can participate in the study in spite of refusing video recordings. The recordings will be stored in a locked file cabinet and treated as confidentially as all other study documents.

